#### 10.54 Second Malignancy

A second malignancy is one unrelated to the treatment of a prior malignancy (and is NOT a metastasis from the initial malignancy). Second malignancies require ONLY routine reporting unless otherwise specified.

#### 10.55 Pregnancy, Fetal Death, and Death Neonatal

If a female subject (or female partner of a male subject) taking investigational product becomes pregnant, the subject taking should notify the Investigator, and the pregnant female should be advised to call her healthcare provider immediately. The patient should have appropriate follow-up as deemed necessary by her physician. If the baby is born with a birth defect or anomaly, a second expedited report is required.

Prior to obtaining private information about a pregnant woman and her infant, the investigator must obtain consent from the pregnant woman and the newborn infant's parent or legal guardian before any data collection can occur. A consent form will need to be submitted to the IRB for these subjects if a pregnancy occurs. If informed consent is not obtained, no information may be collected.

In cases of fetal death, miscarriage or abortion, the mother is the patient. In cases where the child/fetus experiences a serious adverse event other than fetal death, the child/fetus is the patient.

NOTE: When submitting Mayo Expedited Adverse Event Report reports for "Pregnancy", "Pregnancy loss", or "Neonatal loss", the potential risk of exposure of the fetus to the investigational agent(s) or chemotherapy agent(s) should be documented in the "Description of Event" section. Include any available medical documentation. Include this form:

#### 10.551 Pregnancy

Pregnancy should be reported in an expedited manner as **Grade 3 "Pregnancy, puerperium and perinatal conditions - Other (pregnancy)"** under the Pregnancy, puerperium and perinatal conditions SOC. Pregnancy should be followed until the outcome is known.

#### 10.552 Fetal Death

Fetal death is defined in CTCAE as "A disorder characterized by death in utero; failure of the product of conception to show evidence of respiration, heartbeat, or definite movement of a voluntary muscle after expulsion from the uterus, without possibility of resuscitation."

Any fetal death should be reported expeditiously, as **Grade 4 "Pregnancy, puerperium and perinatal conditions - Other**

**(pregnancy loss)**” under the Pregnancy, puerperium and perinatal conditions SOC.

#### 10.553 Death Neonatal

Neonatal death, defined in CTCAE as “A disorder characterized by cessation of life occurring during the first 28 days of life” that is felt by the investigator to be at least possibly due to the investigational agent/intervention, should be reported expeditiously.

A neonatal death should be reported expeditiously as **Grade 4 “General disorders and administration - Other (neonatal loss)”** under the General disorders and administration SOC.

10.554 Corneal epitheliopathy is considered as AE of special interest. Specific dose modification schemes are defined in the Protocol. An alternative severity grading system for corneal epitheliopathy will be used in addition to the CTCAE criteria, since the CTCAE may not adequately capture the severity of these novel adverse reactions (see Table 7–9 and Table 7– 10). The relationship to treatment and the intensity of corneal epitheliopathy will be determined by the investigator, in consultation with the ophthalmologist, using the terms and definitions given in Section 9.6.1.2. There is no need for expedited reporting to report corneal epitheliopathy, unless it meets the criteria for an SAE; however these events will need to be closely monitored.

### 10.6 Required Routine Reporting

#### 10.61 Baseline and Adverse Events Evaluations

Pretreatment symptoms/conditions to be graded at baseline and adverse events to be graded at each evaluation. Grading is per CTCAE v4.0 **unless** alternate grading is indicated in the table below:

| CTCAE System Organ Class (SOC)                       | Adverse Event/
Symptoms | Baseline | Each Evaluation |
|--|----------------------------|----------|-----------------|
| General disorders and site administration conditions | Fatigue                    | x        | x               |
|  | Fever                      | x        | x               |
|  | Flu-like symptoms          | x        | x               |
| Skin and subcutaneous tissue disorders               | Rash maculo-papular        | x        | x               |
|  | Pruritus                   | x        | x               |
| Gastrointestinal disorders                           | #stools each day           | x        |                 |
|  | diarrhea                   |          | x               |
|  | nausea                     | x        | x               |
|  | vomiting                   | x        | x               |

| CTCAE System Organ Class (SOC)                  | Adverse Event/
Symptoms | Baseline | Each Evaluation |
|---|----------------------------|----------|-----------------|
| Respiratory, thoracic and mediastinal disorders | dyspnea                    | x        | x               |

10.62 Submit via appropriate MCCC Case Report Forms (i.e., paper or electronic, as applicable) the following AEs experienced by a patient and not specified in Section 10.6:

10.621 Grade 2 AEs deemed *possibly, probably, or definitely* related to the study treatment or procedure.

10.622 Grade 3 and 4 AEs regardless of attribution to the study treatment or procedure.

10.623 Grade 5 AEs (Deaths)

- Any death within 30 days of the patient’s last study treatment or procedure regardless of attribution to the study treatment or procedure.
- Any death more than 30 days after the patient’s last study treatment or procedure that is felt to be at least possibly treatment related must also be submitted as a Grade 5 AE, with a CTCAE type and attribution assigned.

10.7 Late Occurring Adverse Events

Refer to the instructions in the Forms Packet (or electronic data entry screens, as applicable) regarding the submission of late occurring AEs following completion of the Active Monitoring Phase (i.e., compliance with Test Schedule in Section 4.0).

Report to Bayer: All SAE reports regardless of suspected causality on the date of receipt or within 24 hours after learning of the event by Investigator/Sponsor:

**Electronic Mailbox:** [REDACTED]

**Facsimile:** [REDACTED]

**Address:** Global Pharmacovigilance - USA

**Mail only:** [REDACTED]

**Address:** [REDACTED]

**FDX or UPS only:** [REDACTED]

**Phone:** [REDACTED]

## 11.0 Treatment Evaluation Using RECIST Guideline

NOTE: This study uses protocol RECIST v1.1 template dated 2/16/2011. See the footnote for the table regarding measurable disease in Section 11.44, as it pertains to data collection and analysis.

Response and progression will be evaluated in this study using the new international criteria proposed by the revised Response Evaluation Criteria in Solid Tumors (RECIST) guidelines (version 1.1). Changes in the largest diameter (unidimensional measurement) of the tumor lesions and the short axis measurements in the case of lymph nodes are used in the RECIST guideline.

### 11.1 Schedule of Evaluations:

For the purposes of this study, patients should be reevaluated every 6 weeks. In addition to a baseline scan, confirmatory scans should also be obtained at least 4 weeks following initial documentation of objective response.

### 11.2 Definitions of Measurable and Non-Measurable Disease

#### 11.21 Measurable Disease

11.211 A non-nodal lesion is considered measurable if its longest diameter can be accurately measured as  $\geq 2.0$  cm with chest x-ray, or as  $\geq 1.0$  cm with CT scan or MRI.

11.212 A superficial non-nodal lesion is measurable if its longest diameter is  $\geq 1.0$  cm in diameter as assessed using calipers (e.g. skin nodules) or imaging. In the case of skin lesions, documentation by color photography, including a ruler to estimate the size of the lesion, is recommended.

11.213 A malignant lymph node is considered measurable if its short axis is  $\geq 1.5$  cm when assessed by CT scan (CT scan slice thickness recommended to be no greater than 5 mm).

**NOTE:** Tumor lesions in a previously irradiated area are not considered measurable disease.

#### 11.22 Non-Measurable Disease

11.221 All other lesions (or sites of disease) are considered non-measurable disease, including pathological nodes (those with a short axis  $\geq 1.0$  to  $< 1.5$  cm). Bone lesions, leptomeningeal disease, ascites, pleural/pericardial effusions, lymphangitis cutis/pulmonis, inflammatory breast disease, and abdominal masses (not followed by CT or MRI), are considered as non-measurable as well.

NOTE: 'Cystic lesions' thought to represent cystic metastases can be considered as measurable lesions, if they meet the definition of measurability described above. However, if non-cystic lesions are present in the same patient, these are preferred for selection as target lesions. In addition, lymph nodes that have a short axis  $< 1.0$  cm are considered non-pathological (i.e., normal) and should not be recorded or followed.

### 11.3 Guidelines for Evaluation of Measurable Disease

#### 11.31 Measurement Methods:

- All measurements should be recorded in metric notation (i.e., decimal fractions of centimeters) using a ruler or calipers.
- The same method of assessment and the same technique must be used to characterize each identified and reported lesion at baseline and during follow-up. For patients having only lesions measuring at least 1 cm to less than 2 cm must use CT imaging for both pre- and post-treatment tumor assessments.
- Imaging-based evaluation is preferred to evaluation by clinical examination when both methods have been used at the same evaluation to assess the antitumor effect of a treatment.

#### 11.32 Acceptable Modalities for Measurable Disease:

- Conventional CT and MRI: This guideline has defined measurability of lesions on CT scan based on the assumption that CT slice thickness is 5 mm or less. If CT scans have slice thickness greater than 5 mm, the minimum size for a measurable lesion should be twice the slice thickness.
- As with CT, if an MRI is performed, the technical specifications of the scanning sequences used should be optimized for the evaluation of the type and site of disease. The lesions should be measured on the same pulse sequence. Ideally, the same type of scanner should be used and the image acquisition protocol should be followed as closely as possible to prior scans. Body scans should be performed with breath-hold scanning techniques, if possible.
- Chest X-ray: Lesions on chest x-ray are acceptable as measurable lesions when they are clearly defined and surrounded by aerated lung. However, CT scans are preferable.
- Physical Examination: For superficial non-nodal lesions, physical examination is acceptable, but imaging is preferable, if both can be done. In the case of skin lesions, documentation by color photography, including a ruler to estimate the size of the lesion, is recommended.

#### 11.33 Measurement at Follow-up Evaluation:

- A subsequent scan must be obtained at least 4 weeks following initial documentation of an objective status of either complete response (CR) or partial response (PR).
- In the case of stable disease (SD), follow-up measurements must have met the SD criteria at least once after study entry at a minimum interval of 6 weeks (see Section 11.44).
- The cytological confirmation of the neoplastic origin of any effusion that appears or worsens during treatment when the measurable tumor has met criteria for response or stable disease is mandatory to differentiate between

response or stable disease (an effusion may be a side effect of the treatment) and progressive disease.

- Cytologic and histologic techniques can be used to differentiate between PR and CR in rare cases (e.g., residual lesions in tumor types such as germ cell tumors, where known residual benign tumors can remain.)

## 11.4 Measurement of Effect

### 11.41 Target Lesions & Target Lymph Nodes

- Measurable lesions (as defined in Section 11.21) up to a maximum of 5 lesions, representative of all involved organs, should be identified as “Target Lesions” and recorded and measured at baseline. These lesions can be non-nodal or nodal (as defined in 11.21), where no more than 2 lesions are from the same organ and no more than 2 malignant nodal lesions are selected.

**Note:** If fewer than 5 target lesions and target lymph nodes are identified (as there often will be), there is no reason to perform additional studies beyond those specified in the protocol to discover new lesions.

- Target lesions and target lymph nodes should be selected on the basis of their size, be representative of all involved sites of disease, but in addition should be those that lend themselves to reproducible repeated measurements. It may be the case that, on occasion, the largest lesion (or malignant lymph node) does not lend itself to reproducible measurements in which circumstance the next largest lesion (or malignant lymph node) which can be measured reproducibly should be selected.
- Baseline Sum of Dimensions (BSD): A sum of the longest diameter for all target lesions plus the sum of the short axis of all the target lymph nodes will be calculated and reported as the baseline sum of dimensions (BSD). The BSD will be used as reference to further characterize any objective tumor response in the measurable dimension of the disease.
- Post-Baseline Sum of the Dimensions (PBSD): A sum of the longest diameter for all target lesions plus the sum of the short axis of all the target lymph nodes will be calculated and reported as the post-baseline sum of dimensions (PBSD). If the radiologist is able to provide an actual measure for the target lesion (or target lymph node), that should be recorded, even if it is below 0.5 cm. If the target lesion (or target lymph node) is believed to be present and is faintly seen but too small to measure, a default value of 0.5 cm should be assigned. If it is the opinion of the radiologist that the target lesion or target lymph node has likely disappeared, the measurement should be recorded as 0 cm.
- The minimum sum of the dimensions (MSD) is the minimum of the BSD and the PBSD.

#### 11.42 Non-Target Lesions & Non-Target Lymph Nodes

Non-measurable sites of disease (Section 11.22) are classified as non-target lesions or non-target lymph nodes and should also be recorded at baseline. These lesions and lymph nodes should be followed in accord with 11.433.

#### 11.43 Response Criteria

11.431 All target lesions and target lymph nodes followed by CT/MRI/Chest X-ray/physical examination must be measured on re-evaluation at evaluation times specified in Section 11.1. Specifically, a change in objective status to either a PR or CR cannot be done without re-measuring target lesions and target lymph nodes.

**Note:** Non-target lesions and non-target lymph nodes should be evaluated at each assessment, especially in the case of first response or confirmation of response. In selected circumstances, certain non-target organs may be evaluated less frequently. For example, bone scans may need to be repeated only when complete response is identified in target disease or when progression in bone is suspected.

#### 11.432 Evaluation of Target Lesions

Complete Response (CR): All of the following must be true:

- a. Disappearance of all target lesions.
- b. Each target lymph node must have reduction in short axis to <1.0 cm.

Partial Response (PR): At least a 30% decrease in PBSD (sum of the longest diameter for all target lesions plus the sum of the short axis of all the target lymph nodes at current evaluation) taking as reference the BSD (*see* Section 11.41).

Progression (PD): At least one of the following must be true:

- a. At least one new malignant lesion, which also includes any lymph node that was normal at baseline (< 1.0 cm short axis) and increased to  $\geq$  1.0 cm short axis during follow-up.
- b. At least a 20% increase in PBSD (sum of the longest diameter for all target lesions plus the sum of the short axis

of all the target lymph nodes at current evaluation) taking as reference the MSD (Section 11.41). In addition, the PBSD must also demonstrate an absolute increase of at least 0.5 cm from the MSD.

Stable Disease (SD): Neither sufficient shrinkage to qualify for PR, nor sufficient increase to qualify for PD taking as reference the MSD.

#### 11.433 Evaluation of Non-Target Lesions & Non-target Lymph Nodes

Complete Response (CR): All of the following must be true:

- a. Disappearance of all non-target lesions.
- b. Each non-target lymph node must have a reduction in short axis to <1.0 cm.

Non-CR/Non-PD: Persistence of one or more non-target lesions or non-target lymph nodes.

Progression (PD): At least one of the following must be true:

- a. At least one new malignant lesion, which also includes any lymph node that was normal at baseline (< 1.0 cm short axis) and increased to  $\geq 1.0$  cm short axis during follow-up.
- b. Unequivocal progression of existing non-target lesions and non-target lymph nodes. (NOTE: Unequivocal progression should not normally trump target lesion and target lymph node status. It must be representative of overall disease status change.)

#### 11.44 Overall Objective Status

The overall objective status for an evaluation is determined by combining the patient's status on target lesions, target lymph nodes, non-target lesions, non-target lymph nodes, and new disease as defined in the following table:

| Target Lesions & Target Lymph Nodes | Non-Target Lesions & Non-Target Lymph Nodes                 | New Sites of Disease | Overall Objective Status |
|-------------------------------------|---|----------------------|--------------------------|
| CR                                  | CR  | No                   | CR                       |
| CR                                  | Non-CR/Non-PD   | No                   | PR                       |
| PR                                  | CR
Non-CR/Non-PD   | No                   | PR                       |
| CR/PR                               | Not All Evaluated*  | No                   | PR**                     |
| SD                                  | CR
Non-CR/Non-PD
Not All Evaluated*                   | No                   | SD                       |
| Not all Evaluated                   | CR
Non-CR/Non-PD
Not All Evaluated*                   | No                   | Not Evaluated (NE)       |
| PD                                  | Unequivocal PD
CR
Non-CR/Non-PD
Not All Evaluated* | Yes or No            | PD                       |
| CR/PR/SD/PD/Not all Evaluated       | Unequivocal PD  | Yes or No            | PD                       |
| CR/PR/SD/PD/Not all Evaluated       | CR
Non-CR/Non-PD
Not All Evaluated*                   | Yes                  | PD                       |

\*See Section 11.431

\*\* NOTE: This study uses the protocol RECIST v1.1 template dated 2/16/2011. For data collection and analysis purposes the objective status changed from SD to PR in the NCCTG protocol RECIST v1.1 template as of 2/16/2011 and to match RECIST v1.1 requirements.

11.45 Symptomatic Deterioration: Patients with global deterioration of health status requiring discontinuation of treatment without objective evidence of disease progression at that time, and not either related to study treatment or other medical conditions, should be reported as PD due to “symptomatic deterioration.” Every effort should be made to document the objective progression even after discontinuation of treatment due to symptomatic deterioration. A patient is classified as having PD due to “symptomatic deterioration” if any of the following occur that are not either related to study treatment or other medical conditions:

- Weight loss >10% of body weight.
- Worsening of tumor-related symptoms.
- Decline in performance status of >1 level on ECOG scale.

**12.0 Descriptive Factors**

12.1 Number of prior regimens  $\leq 2$  versus  $> 2$

12.2 Dose Level

To be assigned by Registration Office: -1 vs. 1 vs. 2

### 13.0 Treatment/Follow-up Decision at Evaluation of Patient

#### 13.1 Continuation of treatment

Patients who are CR, PR, or SD will continue treatment per protocol.

#### 13.2 Progressive disease (PD)

Patients who develop PD while receiving therapy will go to the event-monitoring phase.

#### 13.3 Off protocol treatment

Patients who go off protocol treatment for reasons other than PD will go to the event-monitoring phase per Section 4.0.

#### 13.4 CNS PD

Patients who develop PD in the CNS only should receive local therapy and continue treatment on study after completion of local therapy for up to a total of 6 cycles.

#### 13.5 Non-CNS PD

Patients who develop non-CNS PD at any time should go to event monitoring. These patients should be treated with alternative chemotherapy if their clinical status is good enough to allow further therapy.

#### 13.6 Inevaluable patients

If a patient fails to complete the first cycle (21 days) of treatment for reasons other than toxicity, the patient will be regarded as inevaluable and will be replaced during the phase I portion of the trial.

#### 13.7 Ineligible

A patient is deemed *ineligible* if after registration, it is determined that at the time of registration, the patient did not satisfy each and every eligibility criteria for study entry. The patient may continue treatment off-protocol at the discretion of the physician as long as there are no safety concerns, and the patient was properly registered. The patient will go directly to the event-monitoring phase of the study (or off study, if applicable).

- If the patient received treatment, all data up until the point of confirmation of ineligibility must be submitted. Event monitoring will be required per Section 4.0 of the protocol.
- If the patient never received treatment, on-study material must be submitted. Event monitoring will be required per Section 4.0 of the protocol.

#### 13.8 Major violation

A patient is deemed a *major violation*, if protocol requirements regarding treatment in cycle 1 of the initial therapy are severely violated that evaluability for primary end point is questionable. All data up until the point of confirmation of a major violation must be submitted. The patient will go directly to the event-monitoring phase of the study. The patient may continue treatment off-protocol at the discretion of the physician as long as there are no safety concerns, and the patient was properly registered. Event monitoring will be required per Section 4.0 of the protocol.

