| Statistical Analysis | 
Sample Size Assumptions / Target Number of Valid Cases
 
A Simon two-stage design will be used in which a 20% response rate is considered not promising, a 40% response rate is considered promising, and the probabilities of a type I error (falsely accepting a nonpromising therapy) and type II error (falsely rejecting a promising therapy) are set at 0.10 and 0.10, respectively. In this scenario, the maximum trial size would be 37 patients. In the first stage of this design, 17 patients will be accrued (this will include the patients treated at the MTD from the phase I component). If 3 responses or less are observed in the first 17 patients, then the trial will be terminated and the treatment deemed not worthy of further study. If at least 4 responses are observed among these 17 patients, then an additional 20 patients will be accrued to the second stage. If 11 or more responses are observed at the end of the trial the treatment will be considered promising. This design yields at least 90% probability of a positive result if the true response rate is at least 40%. A maximum of 12 patients will be accrued to the phase I portion leading to a maximum of 49 patients for this study.
 
Interim Analyses
 
After 17 patients accrued on the phase II portion including patients treated at RP2D
 |
|-----------------------------|---|

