#### 16.33 To identify preliminary evidence of clinical activity (i.e. confirmed response, timed endpoints, etc.). A confirmed response is defined to be a CR or PR noted as the objective status on two consecutive evaluations at least 4 weeks apart. Confirmed response will be evaluated using the first 6 months of treatment. All patients meeting the eligibility criteria who have signed a consent form and have begun treatment will be evaluable for response. Responses will be summarized by simple descriptive summary statistics delineating complete and partial responses as well as stable and progressive disease in this patient population.

The data on time-related variables will be summarized descriptively. These include time until any treatment related toxicity, time until treatment related grade 3+ toxicity, time until hematologic nadirs (ANC, platelets, hemoglobin), time to progression and time to treatment failure, where time to treatment failure is defined as the time from registration to documentation of progression, unacceptable toxicity, or refusal to continue participation by the patient.

Other clinical activity endpoints will also be explored, including overall survival, progression-free survival, etc. overall and by dose level. These endpoints will be more fully explored during the Phase II portion of the

study.

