#### 16.4 Phase II Statistical Design

- 16.41 Interim Analysis: In the expanded cohort part of the trial, 17 patients will be accrued (this will include the patients treated at the MTD from the phase I component). If 3 confirmed responses or less are observed in the first 17 eligible patients, then the trial will be terminated and the treatment deemed not worthy of further study. If at least 4 confirmed responses are observed among these 17 patients, then an additional 20 patients will be accrued to the second stage.
- 16.42 Final Analysis: If 11 or more confirmed responses are observed at the end of the trial in the first 37 eligible patients, the treatment will be considered promising. This design yields at least 90% probability of a positive result if the true response rate is at least 40%.
- 16.43 Over Accrual: If more than the target number of patients are accrued, the additional patients will not be used to evaluate the final decision rule or used in any decision making process. Analyses involving over accrued patients are discussed in Section 16.54.
- 16.44 Other considerations: Adverse events, quality/duration of response, and patterns of treatment failure observed in this study, as well as scientific discoveries or changes in standard care will be taken into account in any decision to terminate the study

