##### 16.51 Primary Outcome Analyses:

- 16.511 Definition: The primary endpoint of this trial is the proportion of patients who achieve a confirmed response. A confirmed response is defined as PR or CR noted as the objective status on two consecutive evaluations at least 4 weeks apart. All patients meeting the eligibility criteria who have signed a consent form and have begun treatment will be evaluable for response, unless they are determined to be a major violation.
- 16.512 Estimation: The proportion of successes will be estimated by the number of successes divided by the total number of evaluable patients. Exact binomial 95% confidence intervals for the true success proportion will be calculated.

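### Eligible, treated patients can leave the primary denominator as major violations on an open-ended judgement, which can bias the response rate upward; the false-positive rate rises only if such patients are also replaced

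*Combined protocol and SAP*

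**What the plan says.** **Primary set.** Section 16.511, like 16.11, takes eligible, consented patients who have begun treatment and says they "will be evaluable for response, unless they are determined to be a major violation". Section 16.512 divides successes by the number evaluable and attaches an exact 95% interval.

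**Definition.** Section 13.8 calls a patient a major violation when cycle 1 treatment requirements are so "severely violated that evaluability for primary end point is questionable". It lists no qualifying deviations, assessor or time limit, and does not require the decision to be made without knowledge of response. Data are submitted only up to confirmation of the violation, and the patient then moves to event monitoring.

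**Decision rule.** Section 16.41 stops the trial "If 3 confirmed responses or less are observed in the first 17 eligible patients". Section 16.42 calls the treatment promising "If 11 or more confirmed responses are observed at the end of the trial in the first 37 eligible patients". Both count eligible patients. Sections 13.7 and 13.8 treat ineligibility and major violation as separate categories.

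**Sample size and replacement.** Section 16.12 counts evaluable patients (43 at most) and allows 6 more for patients needing replacement, without giving the reasons. The explicit replacement rules, in 13.6 and 16.29a, concern phase I.

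**Phase I response.** Section 16.33 has no such exception: "All patients meeting the eligibility criteria who have signed a consent form and have begun treatment will be evaluable for response". Phase I patients treated at the MTD count among the first 17.

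**The concern.** In an open-label single-arm trial, a post-treatment exclusion that rests on judgement can depend on outcome, even without intent. Section 13.8 limits when the violation occurs, not when it is declared. Under the study calendar (Section 4.1, footnote 8) tumour measurements are repeated at odd cycles from cycle 3, so a cycle 1 deviation may be classified when response is already known. Section 16.5 plans no analysis that keeps all eligible treated patients, so a reader of the results could not see what the exclusions did.

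Two things are at stake: the reported rate with its interval, and the go/no-go decision, which can turn on one response at 4 of 17 or 11 of 37. They respond differently to exclusions, because the rate is divided by evaluable patients while the decision is a fixed count among eligible patients.

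**Working it through.** **Inputs.** The Protocol Synopsis (Statistical Analysis) states that "a 20% response rate is considered not promising, a 40% response rate is considered promising", that the type I and type II errors "are set at 0.10 and 0.10, respectively", and that "the maximum trial size would be 37 patients" (17 + 20). The cut-offs are those of 16.41 and 16.42. The documents give no expected number of major violations, so every number excluded below is an assumption. Six is the upper end because 16.12 provides six replacement places.

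**Step 1. Reproduce the design.** Let b(x; n, p) be the binomial probability. Then

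P(promising | p) = Σ from x = 4 to 17 of b(x; 17, p) × P(Bin(20, p) ≥ 11 − x).

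- p = 0.20: 0.0948, within the 0.10 limit, with 0.10 − 0.0948 = 0.0052 to spare.
- p = 0.40: 0.9033, meeting the stated 90%.

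**Step 2. The estimate.** Suppose 10 responses among 37 eligible treated patients, with k non-responders then excluded. The estimate is 10/(37 − k), with Clopper-Pearson limits:

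| Excluded | Estimate | 95% CI |
|---|---|---|
| 0 | 10/37 = 27.0% | 13.8 to 44.1 |
| 3 | 10/34 = 29.4% | 15.1 to 47.5 |
| 6 | 10/31 = 32.3% | 16.7 to 51.4 |

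This needs no replacement. The smallest promising result is 11/37 = 29.7%, so with six exclusions a trial that fails on its count (10) would report a higher rate than one that just passes.

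**Step 3. The decision, without replacement.** If 16.41 and 16.42 are applied as worded, an excluded non-responder still holds a place among the eligible patients and contributes no response. The count against 4 and 11 is unchanged, so the type I error stays at 0.0948 for any number of excluded non-responders.

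**Step 4. The decision, with selective replacement.** If k stage 1 non-responders are dropped and their places refilled, stage 1 in effect draws responses from 17 + k patients:

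P = Σ from x = 4 to 17 + k of b(x; 17 + k, p) × P(Bin(20, p) ≥ 11 − x).

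| k | Type I error at p = 0.20 |
|---|---|
| 0 | 0.095 |
| 1 | 0.113 |
| 2 | 0.132 |
| 3 | 0.153 |
| 4 | 0.175 |
| 6 | 0.223 |

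This is a worst case, since every exclusion is a non-responder. If instead each non-responder has probability d of being dropped and replaced, the rate among those counted is 0.20/(0.20 + 0.80(1 − d)). Putting that into the Step 1 formula gives 0.099 at d = 1%, 0.104 at 2%, 0.119 at 5% and 0.148 at 10%.

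**Step 5. Exclusion unrelated to response.** With replacement the type I error stays at 0.0948. Without it, and with the cut-offs kept, losing one patient per stage leaves 16 + 19 and gives a type I error of 0.067 and power of 0.858.

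**Step 6. Is replacement planned?** Section 16.12 can be read that way: evaluable patients, with six spare places. Sections 16.41 and 16.42 point the other way. The totals do not decide it, because 16.12 reaches 49 as 43 + 6 while the Synopsis reaches 49 as 12 + 37 with no replacement places.

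**The case against.** A reader might infer that the exclusion by itself raises the false-positive rate above 0.10. The documents do not support that. The rule counts responses among eligible patients, a major violation remains eligible, and no section says that major violations are replaced in phase II. Step 3 shows no increase on that reading. Even with replacement, the increase requires exclusions that favour non-responders. This part of the objection stands, and the type I error claim is conditional.

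A reader might also suppose that patients who do badly in cycle 1 are the natural candidates. That mechanism is weak. Both drugs are given once per cycle, on Day 1, so cycle 1 dosing is normally complete before a patient can deteriorate. The main exception is an infusion reaction, and acting on one as Section 8.13 sets out is not a violation. The cycle 1 deviation also precedes any response data. What remains is late classification, which the text leaves open.

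The difference between 16.33 and 16.511 is not a contradiction. The first serves a descriptive phase I objective and the second the phase II primary endpoint. It is wording to align, since MTD patients enter both.

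Finally, excluding major violations is a pre-specified choice. But a pre-specified category whose membership is left to an undated, unmasked judgement gives little protection, and the effect on the estimate in Step 2 does not depend on replacement.

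**Conclusion.** The point holds for the estimate and conditionally for the decision. Followed as written, the plan allows eligible treated patients to be removed from the primary denominator on an open-ended judgement that may be made with response known. If those removed are non-responders, the rate and its interval move up: by 2.4 percentage points for three exclusions from 10/37 and 5.3 for six. The number and direction of exclusions are assumptions.

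The type I error exceeds 0.10 only if exclusions favour non-responders and the excluded patients are replaced. In that worst case one early replacement is enough (0.113) and four give about 0.175. The documents neither state nor rule out replacement. The mismatch between eligible in 16.41 and 16.42 and evaluable in 16.12 and 16.512 should be resolved in its own right, because the decision and the reported rate can currently rest on different patients.

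**What to change.** - In 16.11 and 16.511, delete the major-violation exception for the primary decision and estimate.
- Use one population in 16.11, 16.12, 16.41, 16.42, 16.511 and 16.512: all eligible patients who began treatment, counted as non-responders if no confirmed response is observed. Align 16.33 and the Synopsis denominator with it.
- State that major violations are not replaced in the 17 and 37, and list the reasons for which the six places in 16.12 may be used.
- Report the set without major violations as a sensitivity analysis, giving the number excluded and their responses.

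With p = 0.20 and 0.40 read as rates in this population, the design keeps its type I error of 0.0948 and power of 0.9033. The cost is wording, one extra table and possibly a slightly lower stated response rate. The 17/37 design needs no additional patients.
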